This study manipulates e-cigarette nicotine flux systematically, testing the hypothesis that abuse liability will be related directly to flux among a sample of cigarette smokers. No previous study has manipulated nicotine flux and examined within-group effects, so we could not estimate effect size. Thus, we calculated a sample size to achieve a power of >0.80 with $\alpha <0.05$ and assuming a small effect size (Cohen's $f=0.20$) and moderate repeated measures correlation ($r=0.5$) in a repeated measures ANOVA with nicotine flux as within-subjects factors (N=32; GPower). In Study 2, 40 cigarette users will attend the lab for 5 sessions - no flux, low flux, cigarette-like flux, high flux, and an own brand cigarette control (always session 5). We hypothesize that flux will be positively associated with willingness to pay/work (drug purchase task, progressive ratio task) and willingness to substitute e-cigarettes for own brand cigarettes (cross-product drug purchase task, cross-product progressive ratio task), and inversely to price sensitivity (drug purchase task) for all smokers.

It is possible that we would consent up to 100 participants in order to obtain 40 participants who complete the entire study.

4. * List the study inclusion criteria:

All participants must be healthy (determined by self-report), between the ages of 18-55 (verified by photo ID), willing to provide informed consent, and attend the lab and abstain from tobacco/nicotine as required. Participants must agree to use designated products according to the study protocol.

Participants must use at least 5 cigarettes per day if they are not classified as dual users of inhaled tobacco products.

Participants classified as dual users of inhaled tobacco products must meet at least of two definitions described below:

- at least some day use of cigarettes (≥ 3 days per week at any cigarettes per day frequency) AND
- daily use of another inhaled tobacco product (e.g., e-cigarettes, cigars, pipe)

OR

- daily use of cigarettes (at any cigarettes per day frequency) AND
- at least some day use of another inhaled tobacco product (e.g., e-cigarettes, cigars, pipe; ≥ 3 days per week at any frequency).

Participants must have a 'positive' cotinine cassette result to verify nicotine use.

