Please note that beginning July 1, 2020, per HB1570, we will recruit individuals aged 18-55. This law "Provides an exception to the law prohibiting possession of tobacco products, nicotine vapor products, or alternative nicotine products by a person less than 21 years of age when such possession is part of a scientific study being conducted by an organization for the purpose of medical research to further efforts in cigarette and tobacco use prevention and cessation and tobacco product regulation, provided that such medical research has been approved by an institutional review board pursuant to applicable federal regulations or by a research review committee." We will not enroll any participants under the age of 21 until after July 1, 2020.

5. * List the study exclusion criteria:

Individuals with the following self-reported current, diagnosed medical condition(s) will be excluded automatically: uncontrolled high blood pressure (i.e., self-reported and/or observed at screening; BP above 160/100), recent heart attack/stroke, coronary heart disease, severe immune system disorders (e.g., HIV/AIDS, multiple sclerosis), respiratory disorders (e.g., COPD, asthma), kidney diseases, liver diseases (e.g., cirrhosis), or seizures.

Individuals with other self-reported current, diagnosed medical conditions (e.g., diabetes, thyroid disease, lyme disease) will be considered for exclusion after consultation with the PI and medical monitor. Participants with any medical condition/medication that may affect participant safety, study outcomes, or biomarker data will be excluded based on these consultations.

Participants with self-reported current, diagnosed psychiatric conditions, and who are currently under the care of a physician for psychiatric conditions, or who report current psychiatric treatment or psychotropic medication use will be excluded.

Individuals with past-month use of other illicit drugs including cocaine, opioids, benzodiazepines, and methamphetamine will be excluded.

Individuals who report using marijuana ≥ 16 days in the past 30 and/or alcohol ≥ 26 days in the past 30 days will be excluded.

Those who intend to quit tobacco/nicotine use in the next 30 days will be excluded and referred to cessation treatment.

Use of other tobacco products (other than cigarettes) at any frequency will NOT be exclusionary.

Women will be excluded if they are breast-feeding or test positive for pregnancy (by urinalysis) at the screening.

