Recruitment and Enrollment. Potential participants will be recruited by IRB-approved advertisements, as well as referral from current participants. Once initial screening is completed (either over the phone or via the internet), potentially eligible participants will be invited to the lab to complete in-person informed consent, additional screening, and familiarization with study procedures (approximately 2 hrs, \$15 compensation). Once participants have been seated in a private study room, research staff will communicate with the participants primarily using Zoom as an intercom, to speak/interact with participants. Prior to in-person data collection, staff will review the informed consent in person and/or using a Powerpoint/video tool to ensure they understand the study, its risks and benefits, and their rights as research participants. Participants will have the opportunity to ask questions to the research staff, prior to signing the consent document. Following documentation of informed consent, participants will complete baseline measures to confirm eligibility, have their blood pressure and heart rate checked, provide a urine sample that will be tested for cotinine level (to confirm current smoking status) and pregnancy (women only), and provide a exhaled breath carbon monoxide (eCO) sample. Age will be verified by asking participants to provide some form of identification that includes a date of birth. Photos of participant cigarette packs will be taken. All study procedures will be reviewed/practiced using approved measures and/or Powerpoint/video-based tools. Participants will complete the Minute Discounting Task and finally the Balloon Analogue Risk Task (BART). Depending upon task performance, participants will receive up to \$40 in compensation for the actual amount earned at the end of the BART task.

New recruits will replace participants who do not complete the study. Accrual ends when the required number of completers (N=40) is reached.

Individuals whose blood pressure levels are elevated (>=140 mmHg systolic or >=90 mmHg diastolic) during screening or at a session will be provided with a blood pressure information sheet by the research staff (see study document). This sheet will be provided at the first instance of elevated blood pressure observed during the study.

Products. Own brand tobacco cigarettes will be purchased locally following enrollment by VCU approved staff. For all

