other sessions we will provide ECIG liquid at 0 mg/ml, 6 mg/ml, 15 mg/ml, or 30 mg/ml; nicotine and an “open system” ECIG (e.g., Kanger Sub Box Mini C; ECIG device modified by Project 1 team) set to 30 watts. All liquids used will be unflavored and unsweetened. ECIG puffs will be limited to 2 seconds in duration for all of these sessions using hardware and/or a computer program. Own brand cigarette puffs will be allowed to vary in duration (not controlled).

Procedure. The first four sessions will be identical, except for the product given to the participant. The fifth session will be their own brand session. This session will end early, as described below.

Each session, participants will be asked to refrain from tobacco/nicotine use for ≥ 12 hours and drinking caffeinated beverages for 1 hour prior to their scheduled session with verification of tobacco/nicotine use status upon arrival at the laboratory for each session. More specifically, upon arrival at the laboratory for each session, participants’ breath eCO will be measured to ensure compliance with the overnight abstinence criteria (eCO must be either < or equal to half of the eCO [ppm] that the participant had at the in-person screening visit, or, if 10 ppm or less at screening, it must be equal to or less than 5 ppm before a session can begin). We are no longer requiring 1-hr food abstinence prior to each session as this design detail was originally included to reduce the impact of a recent meal/caloric intake on primary outcomes/participant responding. We reconsidered this design detail in consultation with our study timeline and other protocols ongoing among our research team and decided that this food abstinence requirement likely has less impact than that from caffeine consumption on our primary outcomes and is more burdensome to participants. Research staff will use Zoom, as an intercom to communicate with participants whenever possible during sessions.

At the start of the session, participants will be asked about symptoms experienced since last visit and their use of other substances in their ECIG. Answers given about respiratory and gastrointestinal symptoms will be compared to the participants’ previous answers, and if any symptoms have become more frequent or more severe, [name] will be asked to review the symptoms. In some cases, we may contact [name] to determine if a session can proceed.

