Next, participants will have their breath tested (eCO) to assess compliance and physiologic data collection will begin. We will check blood pressure once at the beginning of the session and again at the end. Heart rate will be measured continuously throughout the session.

Approximately five minutes after session onset, participants will sample the session-specific product (4 puffs) followed by a 60-minute rest period. During this time participants will not be allowed to eat or drink outside beverages but we will provide water to drink and they are invited to use their phone, read books/magazines, or watch movies that we provide to them.

After the rest period, participants will complete baseline subjective measures 1 to assess tobacco abstinence symptoms. Immediately after subjective measures 1, two DPTs (session specific DPT, CP-DPT) will be completed. The DPTs take approximately 10 minutes to complete. Then the PRT will begin, which lasts for 30 minutes. Subjective measures 2 begins at 30 minutes post-PRT start. This should take approximately 5 minutes. After this participants will start the 2nd 60-minute rest period.

After the rest period, participants will complete subjective measures 3. This should take about 5 minutes. Then participants will start the CP-PRT, which lasts for 30 minutes. Subjective measures 4 begins at 30 minutes post-CP-PRT start.

When the CP-PRT and Subjectives measures 4 are completed, physio data collection will end and participants will be paid for their time. The study procedures for sessions 1 – 4 should take no more than 220 minutes or 3 hours and 40 minutes.

For the 5th session, participants will experience the same procedures except they will not complete the CP-DPT or CP-PRT. Thus study procedures for the 5th session should take no more than 185 minutes or 3 hours 5 minutes.

Please note there can be some variability in the session times due to participant behavior (i.e., taking shorter/longer than expected to complete measures/tasks).

Session Timeline:

0m – eCO Check; Physiologic data collection begins, additional questions asked.

5m – 4 sample puffs

10m – Begin 60m rest period

70m – Subjectives measure 1

75m – DPTs – 2: session specific DPT, CP-DPT with their own brand cigs

85m – PRT – 30 min

115m – PRT completed; Subjectives measure 2

120m – Begin 60m rest period

180m – Subjectives measure 3

185m – own brand session STOP

OR

185m – CP-PRT – 30 min

215m – CP-PRT completed; Subjectives measure 4

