9. The researchers will let you know about any significant new findings (such as additional risks or discomforts) that may make you change your mind about participating in the study.

Non-physical Risks

1. Participation in research might involve some loss of privacy. There is a small risk that someone outside the study could see and misuse information about you.
2. The study questionnaires ask personal questions that are sensitive in nature. You may refuse to answer any question that makes you feel uncomfortable.

3. * Will the intervention activity be physically invasive or painful?

Yes
 No

4. * Describe the impact the intervention activity will have on participants, including the nature and duration of any impact(s):

Participants will be using an ECIG/cigarette that contains nicotine. They may experience the effects of nicotine use which could include acute increases in heart rate and blood pressure, sweating, lightheadedness, dizziness, nausea, and nervousness, although these are less likely in individuals who use nicotine-containing products regularly. All of the participants are experienced, cigarette smokers. The duration of these impacts is expected to be no longer than the length of the session.

5. * In the investigator's opinion, is there any reason to think that the participants will find the intervention activity offensive or embarrassing? Explain why or why not.

No.

Sample Collection Details

1. * Select all of the types of samples that will be collected as part of this study.

- Amniotic Fluid
- Blood
- Buccal Smears
- Saliva
- Tissue
- Urine
- Stool
- Other

2. * If Other, please describe the type of sample being collected:

Upon arrival at the laboratory for the research session, participants' eCO will be measured to ensure compliance with the overnight abstinence criteria. Samples will not be stored.

3. * In order to collect urine, will an indwelling catheter be placed solely for the research study:

- Yes
- No

4. * Describe how the sample will be collected and the collection schedule. For each type of sample, include information about

- The procedures that will be followed to collect the sample
- The role(s) of the individuals who will collect the sample
- The volume/size range of the sample
- The timing and frequency of sample collection

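### The session-entry abstinence check is exhaled CO alone, so a dual user who vapes until arrival is recorded as nicotine-abstinent; the effect on the flux contrasts is probably modest

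*Combined protocol and SAP*

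**What the plan says.** Under Study Procedures, item 6 (Procedure), "participants will be asked to refrain from tobacco/nicotine use for ≥ 12 hours" before each session, and tobacco/nicotine status is to be verified on arrival. The method then given is a single one: "participants’ breath eCO will be measured to ensure compliance with the overnight abstinence criteria". The pass mark is no more than half the screening eCO; alternatively, "if 10 ppm or less at screening, it must be equal to or less than 5 ppm before a session can begin".

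The session sequence repeats the check ("participants will have their breath tested (eCO) to assess compliance and physiologic data collection will begin"), and so does Sample Collection Details, item 2 ("eCO will be measured to ensure compliance with the overnight abstinence criteria. Samples will not be stored"). Neither adds a second method. Urine cotinine, the only nicotine-specific test, is taken at screening only. The session-start questions that are described cover symptoms since the last visit and other substances used in the participant's own e-cigarette. The timeline also lists unspecified additional questions at minute 0.

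Study Population, item 4, accepts as dual users people who smoke on as few as 3 days a week and report "daily use of another inhaled tobacco product (e.g., e-cigarettes, cigars, pipe". Item 5 adds: "Use of other tobacco products (other than cigarettes) at any frequency will NOT be exclusionary".

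Under Risks, Discomforts, Potential Harms and Monitoring, item 5, a participant who has not kept the 12-hour abstinence may reschedule. The number of attempts is not limited, and the text notes that abstinence is hard for some.

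**The concern.** The requirement covers all nicotine, while the check covers only nicotine that arrives with smoke. This is a matter of the analyte and not of the ppm cut-off: no CO threshold shows that someone vaped an hour before arrival. The cut-off adds to the gap. A some-day smoker whose screening eCO is already 5 ppm or less meets the session criterion with no change at all.

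The outcomes are willingness to work or pay for puffs. Recent nicotine could lower that willingness and, if it differs between one person's sessions, would add to the within-person error against which flux is tested. It could also blur the contrast between the 0 mg/ml and the nicotine sessions. Separately, a report based on this plan would say that 12-hour nicotine abstinence was verified when, for users of non-combusted products, it was not.

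**Working it through.** **1. Coverage of the check, from the text.**

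| Product the criteria allow | Combusted? | Registered by eCO? |
|---|---|---|
| Cigarettes | yes | yes |
| Cigars, pipe | yes | yes |
| E-cigarettes, daily use allowed | no | no |
| Other non-combusted tobacco, any frequency | no | no |

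The one premise not written in the documents is that CO comes from combustion. It needs no figure. The gap is confined to the last two rows.

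**2. The plan's own sample size** (Study Population, item 3). For a one-group within-subject ANOVA, λ = f²·N·m/(1−r), with df m−1 and (N−1)(m−1). At f = 0.20, r = 0.5, α = 0.05, m = 5 and N = 32, λ = 0.04 × 32 × 5 / 0.5 = 12.8 on 4 and 124 df, and power is 0.814. At N = 31 it is 0.799. The stated N = 32 is therefore reproduced with five conditions.

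**3. Baseline for the flux test.** For the four e-cigarette conditions and 40 completers, λ = 0.04 × 40 × 4 / 0.5 = 12.8 on 3 and 117 df, and power is 0.852.

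**4. Effect of undetected use, on assumed values.** Model: y = μ(level) + b(person) + e − d·V. Person and error variances are 0.5 each, so total SD = 1 and r = 0.5. The level means are −0.268, −0.089, 0.089 and 0.268, whose SD is 0.20. V marks a violated session and d is the lowering in SD. There were 20,000 simulated trials per cell.

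| Who violates | d = 0.5 SD | d = 1 SD |
|---|---|---|
| Nobody | 0.85 | 0.85 |
| Same 10, 20 or 30% of people, every session | 0.85 | 0.85 |
| 30% of people vape; 10, 20, 30% of their sessions | 0.85, 0.84, 0.84 | 0.83, 0.82, 0.81 |
| 10, 20, 30% of all sessions, at random | 0.83, 0.82, 0.81 | 0.79, 0.73, 0.69 |

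Repeat runs differ by about 0.01, so the third row is best read as 0.80 to 0.85. It corresponds to 0.30 × 0.10 = 3% up to 0.30 × 0.30 = 9% of all sessions. The second row is exact and not a simulation accident: a shift of −d in all four sessions is removed with the person's mean.

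**5. If violators also respond less to flux.** Let a share p of participants keep a fraction k of the effect. As an approximation, average f = 0.20 × (1 − p(1−k)). With k = 0.5 and p = 0.10 to 0.30, f = 0.19 to 0.17 and power is 0.81 to 0.71. With k = 0, f = 0.18 to 0.14 and power is 0.76 to 0.52. Neither p nor k is in the documents, and k = 0 is an extreme.

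**The case against.** Four points on the other side carry weight.

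- **Baseline exposure is partly standardised.** Everyone takes 4 puffs of the session product at minute 5 and rests 60 minutes before the tasks. The grant text gives control of time since last use as a purpose of its similar sampling step. The control is incomplete, because the 0 mg/ml session supplies no nicotine, but it weakens the route from earlier vaping to lower responding.
- **Order is balanced and participants are blinded.** The four e-cigarette sessions follow a Latin square and participants do not know the condition, so vaping before arrival should not track nicotine level. A reader might infer that the flux contrasts are biased. The documents do not support that; an additive effect would mainly be noise.
- **Habitual use may be a stable trait.** In that case an additive shift cancels within the person. This holds only for an additive effect, as step 5 shows.
- **Last use may already be asked.** The minute-0 additional questions are unspecified, and the session forms are separate uploads that are not part of these documents. The rescheduling provision also covers tobacco/nicotine generally and is not tied to an eCO failure. What remains is that the protocol names no such item and attaches no rule to one.

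A further stronger reading concerns screening, where participants "provide a urine sample that will be tested for cotinine level (to confirm current smoking status"; cotinine is also positive from e-cigarettes alone. That is loose wording in one place. The inclusion criteria, the sample-collection section and the risk section all describe cotinine as verifying nicotine use or exposure, and screening also takes eCO and tobacco-use history. It is not a separate defect and has no bearing on session abstinence.

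It is also fair that self-report does not verify abstinence objectively. It is nonetheless a measure that could pick up vaping here without a new assay.

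**Conclusion.** The gap is real on the text: a nicotine-abstinence requirement is verified by a test of combusted tobacco, in a sample that deliberately includes daily vapers. It shows that such participants can pass, not that any do.

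The consequence for the flux contrasts is probably modest. Under the additive assumptions, power at 40 completers runs from an unchanged 0.85 (same people, every session), through 0.80 to 0.85 (30% of participants vaping, 10–30% of their sessions affected), to about 0.73 (20% of all sessions lowered at random by 1 SD). The last case spreads violations over everyone, although only users of non-combusted products can exploit the gap. A reader might conclude that power drops below 80%. That needs such widespread 1 SD shifts, or a share of participants with a weakened flux response, and the documents support neither. They do not exclude them either, since they give no dual-user share and no violation rate.

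What is certain is narrower: as written, the study could not properly claim verified nicotine abstinence for its users of non-combusted products.

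**What to change.** 1. With the session-start questions, record the time of last use of each nicotine product, naming e-cigarettes, or confirm in the protocol that the additional questions already do so. Apply the existing rescheduling provision to reported use within the plan's own 12-hour window.
2. Pre-specify a sensitivity analysis of the flux contrasts restricted to participants with no baseline e-cigarette or other non-combusted use. Patterns of tobacco use are already collected at screening.
3. Reword the Procedure text so that eCO verifies abstinence from combusted tobacco only, with other nicotine covered by self-report.

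The cost is one or two questionnaire items per session, one extra analysis and a wording change, with no new assay or staff. The downsides are that self-report is imperfect, a few more sessions may be rescheduled, and the restricted analysis is smaller by an amount the documents do not let one predict. If sessions have already been completed, items 2 and 3 can still be done.

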220m – End session

Product administration will consist of 4 sample puffs at the beginning of each session. Four behavioral tasks will be performed (DPTs, CP-DPT, PRT, and CP-PRT) for sessions 1 – 4. The PRT and CP-PRT behavioral tasks may yield additional puffs from a session specific ECIG or their own brand cigarette. The CP-PRT and CP-DPT will not be performed in the own-brand session (session 5) but participants will be asked to complete the remaining two behavioral choice tasks (DPT and PRT). See the Behavioral Measures section below for more details.

Three months following the final in-person session, participants will be administered one follow- up survey via phone (verbally administered) or email (participant completes survey online) regarding their cigarette and e-cigarette use behaviors ('Follow-Up Survey').

Measures.

Baseline measures. During the in-person eligibility screening, we will assess sociodemographic information, risk taking,

discounting, health and psychiatric conditions, drug and alcohol use, history and patterns of tobacco use, nicotine dependence/craving, and perceived harm and risk of tobacco products using standardized items from national surveys (e.g., Behavioral Risk Factor Surveillance Survey; Tobacco Use Supplement to the Current Population Survey). We will also take pictures of participant's own brand cigarettes. Urine samples will be tested immediately for cotinine (a major nicotine metabolite) using the NicAlert semi-quantitative test (Jant Pharmaceutical Corporation, Encino, CA), and among women for pregnancy. We will also be obtaining baseline physiological measures including: eCO and HR/BP. eCO will be assessed via a BreathCO monitor (Vitalograph, Lenexa, KS). HR/BP will be measured and saved electronically using software and equipment that sounds an alarm if safety parameters are exceeded (Model 506, Criticare Systems).

Risk tasking and discounting tasks will only be administered to participants at baseline who appear eligible based on all the criteria assessed during the in-person screening. These two tasks will be the final assessments for participants who appear to be eligible at the in-person screening.

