Physiological measures. Physiological measures are being collected primarily for participant safety during sessions. HR/BP will be measured and saved electronically using software and equipment that sounds an alarm if safety parameters are exceeded (Model 506, Criticare Systems).

Behavioral measures. Our primary behavioral measures are four behavioral choice tasks (Progressive Ratio Task, Cross Product-Progressive Ratio Task, Drug Purchase Task, and Cross Product-Drug Purchase Task).

The Progressive Ratio Task (PRT) requires participants to click on a button on a computer to earn puffs of the session-specific ECIG or their own brand cigarettes. Ten key presses are required to earn the first puff, and this number is increased by 30% for each subsequent puff. Once the participant declines to press the button for five minutes then the PRT is considered complete. PRT outcome measures are 1) breakpoint PRT (maximum number of key presses completed to earn a puff), 2) number of puffs self-administered, and 3) latency (sec) to initiate key pressing. Data is collected via a software program created using Python. The data file is stored locally, under a username and password protected profile. It is then copied to secure storage locations (such as Ironkey or R-Drive) after each session.

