Individuals whose BP levels are elevated (≥ 140 mmHg systolic or ≥ 90 mmHg diastolic) during baseline screening or at a session will be provided with a blood pressure information sheet by the research staff (see study document). This sheet will be provided at the first instance of elevated blood pressure observed during the study.

Research personnel are trained to alert the research nurse if heart rate continually exceeds 120 beats per minute, if systolic BP continually exceeds 160 mm Hg, or if diastolic BP continually exceeds 100 mm Hg. Individuals whose heart rate and/or BP levels remain elevated will be monitored by the research nurse and if, necessary, emergency responders will be notified. Emergency medical coverage will be available via the emergency room that is 1.5 miles from the CSCP.

5. * Describe criteria for when the investigator would withdraw an individual participant from the study; such as safety or toxicity concerns, emotional distress, inability to comply with the protocol, etc.:

Participants may be withdrawn from the study if the PI or study nurse has any safety concerns (such as high blood pressure or heart rate) during sessions.

The PI/research nurse and/or Medical Monitor will be consulted/notified via phone/email specifically concerning high

blood pressure observations that occur during any study session to determine whether a participant should remain in the study.

If a participant does not comply with the 12-hour tobacco/nicotine abstinence requirement (which can be difficult for some participants), we allow participants to re-schedule a session. We allow multiple attempts, but do not have a specified number of attempts that are allowed, as it depends on the circumstances of each participant.

6. * Summarize any pre-specified criteria that would trigger the investigator/sponsor/monitoring committee to stop or change the study protocol due to safety concerns:

We do not have any prespecified criteria for stopping or changing the study protocol due to safety concerns.

Data and Safety Monitoring

Data and safety monitoring is a system for checking the study's data at regular intervals over the study period to identify and address issues that could affect the safety of research participants. This requirement is in accordance with 45 CFR 46.111.

The purpose of data and safety monitoring plan is to set forth study team procedures for monitoring/addressing:

- Participant safety (physical, psychological, etc.)
- Data validity

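### No blood-pressure reading is scheduled between the progressive ratio task and the cross-product task, so the 160/100 nurse alert cannot act on scheduled readings in that window

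*Combined protocol and SAP*

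**What the plan says.** All places are in the combined protocol and SAP.

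- **Study Procedures, item 6 (Procedure):** "We will check blood pressure once at the beginning of the session and again at the end". Only heart rate is continuous.
- **Same item (Physiological measures):** "Physiological measures are being collected primarily for participant safety during sessions". The heart-rate and blood-pressure equipment sounds an alarm when safety parameters are exceeded, but no interval for blood-pressure readings is given.
- **Risks, Discomforts, Potential Harms and Monitoring, item 4:** staff alert the research nurse "if systolic BP continually exceeds 160 mm Hg, or if diastolic BP continually exceeds 100 mm Hg", or if heart rate stays above 120 beats per minute. How many readings, or over what time, would count is not stated. The nurse then monitors anyone whose levels remain raised.
- **Same section, item 5:** the investigator, nurse or medical monitor is consulted on high "blood pressure observations that occur during any study session to determine whether a participant should remain in the study".
- **Study Procedures, item 6 (Recruitment and Enrollment):** a pressure of 140/90 or more leads to an information sheet. "This sheet will be provided at the first instance of elevated blood pressure observed during the study".
- **Product use:** there are four sample puffs at about 5 min, and then: "The PRT and CP-PRT behavioral tasks may yield additional puffs from a session specific ECIG or their own brand cigarette". The PRT has no puff limit; the CP-PRT allows at most 10 puffs. On the PRT the text adds: "Once the participant declines to press the button for five minutes then the PRT is considered complete". The questionnaire that follows has a fixed time: "Subjective measures 2 begins at 30 minutes post-PRT start".

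**The concern.** A rule that asks for sustained high pressure needs repeated readings. The schedule gives one reading before product and one at the end, so nothing scheduled can set off the rule after the PRT and before the CP-PRT begins.

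The interval matters because the protocol names acute rises in blood pressure as a possible nicotine effect (Behavioral Intervention/Task Details, items 2 and 4). The PRT is also the one product-use task without a stated puff cap. The screening exclusion applies above 160/100, which is the same level as the alert, so a participant can enrol close to it.

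As scheduled, a participant who goes above 160/100 during the PRT, with no heart-rate alarm and no complaint, would rest for 60 min and start the CP-PRT with no required pressure check. What is at stake is whether a written safety procedure works as intended, not the analysis.

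**Working it through.** **Inputs.** Times come from the Session Timeline in Study Procedures, item 6. The 40 completers and five sessions come from the Overview there.

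**1. Reproduce the stated session lengths.**
- Sessions 1-4: 5 + 5 + 60 + 5 + 10 + 30 + 5 + 60 + 5 + 30 + 5 = 220 min, as stated.
- Session 5, stopping after subjective measures 3: 5 + 5 + 60 + 5 + 10 + 30 + 5 + 60 + 5 = 185 min, as stated.

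**2. Gap from the end of the PRT block to the next scheduled reading.** The block ends at 5 + 5 + 60 + 5 + 10 + 30 = 115 min. The end reading is taken to fall during or just after the last questionnaire.

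| | End reading (min) | After PRT block (min) | After CP-PRT (min) |
|---|---|---|---|
| Sessions 1-4 | 215-220 | 215 - 115 = 100 to 220 - 115 = 105 | 215 - 215 = 0 to 220 - 215 = 5 |
| Session 5 | 180-185 | 180 - 115 = 65 to 185 - 115 = 70 | no CP-PRT |

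If session 5 runs a little shorter because the cross-product purchase task is dropped, both times shift together and the gap is unchanged.

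**3. Gap from the last PRT puff.** A participant can stop early, so the last puff can fall anywhere in 85-115 min.
- Sessions 1-4: 215 - 115 = 100 to 220 - 85 = 135 min.
- Session 5: 180 - 115 = 65 to 185 - 85 = 100 min.

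**4. Count of scheduled readings.** 2 x 5 = 10 per participant, or 400 for 40 completers. Per participant, 5 are before product, 4 are 0-5 min after the CP-PRT, and 1 is 65-70 min after the PRT block. Of 5 x 40 = 200 planned PRTs, none has a scheduled reading in the 65 min after the block ends. Of those 200, 40 use 0 mg/ml liquid.

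**5. How far the PRT is bounded in practice.** The first puff costs 10 presses and each later one 30% more, so n puffs cost 10(1.3^n - 1)/0.3 presses in total. The pressing rate is my assumption, held without pause for 30 min (1,800 s).

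| Presses per second | Presses available | Most puffs | Cost of that many |
|---|---|---|---|
| 3 | 5,400 | 19 | about 4,840 |
| 5 | 9,000 | 21 | about 8,200 |
| 10 | 18,000 | 23 | about 13,880 |

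Time spent puffing lowers these ceilings. They sit comfortably with the protocol's expectation of no more than 40 puffs per session.

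**6. With one added reading at 115-120 min.**
- It comes 0-5 min after the PRT block, and 115 - 115 = 0 to 120 - 85 = 35 min after the last PRT puff.
- A high value repeated 5 min later is known by 120-125 min, which leaves 180 - 125 = 55 to 180 - 120 = 60 min before the rest ends.
- The longest interval between scheduled readings in sessions 1-4 falls from 215-220 min to 115-120 min.

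**The case against.** The strongest reply is that two readings per session are proportionate here. Several safeguards exist:

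- Uncontrolled pressure above 160/100, recent heart attack or stroke, and coronary heart disease are exclusions.
- Participants are regular nicotine users, and the protocol rates these effects as very unlikely.
- Heart rate is continuous with its own alert, the equipment has an alarm, and a full-time nurse is available (stated for seizure risk).
- The nurse's duty to watch levels that remain raised presupposes repeat readings, and nothing forbids staff from taking more.
- Repeated high pressure can lead to withdrawal.

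All of this stands, and it makes the risk low. None of it requires a reading after the PRT or says what counts as continual. The consultation, nurse-monitoring and withdrawal rules act on pressure that someone has already observed. The reading at the start of the next session follows 12 hours of abstinence, so it does not show the level after the previous PRT.

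A reader might infer three stronger points that the documents do not support.

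- *No reading follows product use closely.* In sessions 1-4 the end reading comes 0-5 min after the CP-PRT. The gap concerns the PRT, and the sample puffs before it.
- *PRT exposure is unlimited.* No cap is written, but the escalating cost bounds it in effect, and one of the five sessions uses liquid without nicotine.
- *A high reading at session end goes unmanaged.* The nurse's monitoring of levels that remain raised, with emergency responders called if needed, largely covers this.

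**Conclusion.** The point holds as a modest gap in a safety procedure. After the PRT and before the CP-PRT, scheduled readings cannot set off the 160/100 nurse alert. The next scheduled reading is 100-105 min after the PRT block in sessions 1-4. In session 5, which has no CP-PRT, it is 65-70 min after the block.

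These figures count scheduled readings; they do not measure risk. The documents give no blood-pressure rise or event rate, so no expected number of participants above 160/100 can be derived. Nor do they support a claim that the primary comparisons are affected.

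The conclusion assumes that sessions keep to the timeline and that no other rule schedules a reading. The blood-pressure information sheet and the monitor manual are listed but not reproduced, so cuff intervals or alarm settings may be given there. Confidence is high about the schedule and lower about how much it matters in practice.

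**What to change.** 1. In Study Procedures, item 6, add one blood-pressure reading at about 115 min, with subjective measures 2, in all five sessions. Take it at the same point in the questionnaire block every time, so that it is constant across conditions.
2. In Risks, Discomforts, Potential Harms and Monitoring, item 4, define the blood-pressure alert as two readings above 160 systolic or 100 diastolic taken 5 min apart. Any single high reading triggers the repeat, and a confirmed one goes to the nurse before further product use.

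**Cost.** Five readings per participant, 5 x 40 = 200 for the completers, on the existing monitor. The scheduled total rises from 10 to 15 per participant (400 to 600). The downsides are a brief cuff reading during a questionnaire block and occasional extra nurse calls. The repeat and review fit inside the 60-min rest, so the CP-PRT need not move.

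I would not add a routine reading at 180 min. A high value confirmed at 185 min would delay the CP-PRT, which is a primary behavioural task, and the delay could differ by flux condition. A separate release rule at session end is also unnecessary, given the nurse's existing duty.
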